1.3. Schedule of Assessments

The schedule of assessments is shown in [Table 1](#).

Table 1. Schedule of Assessments

Study Procedure	Screening Period	Treatment Period					Follow-up Period / ET ¹
	Study Days: D -28 to D -1	D1	D2	D3	D4	D5	D35
Study Visits:	V1	V2	V3	V4	V5	V6	V7
Informed consent	X						
Cystoscopy / cold cup biopsy	X						
Inclusion/exclusion criteria	X	X					
ECOG Performance Status	X						
Medical history	X						
Pregnancy test ²	X	X					X
MUGA or ECHO	X						
Chest X-ray or CT scan	X						
Obtain tumor tissue sample ³	X					X	
Hematology ⁴	X	X		X		X	X
Clinical chemistry ⁵	X	X		X		X	X
Urinalysis ⁶	X	X		X			X
Full physical exam ⁷	X						X
Assess for physical symptoms/toxicities ⁷		X	X	X	X	X	
Vital signs ⁸	X	X	X	X	X	X	X
ECG ⁹	X	X				X	X
Adverse events ¹⁰	X	X	X	X	X	X	X
Concomitant medications ¹¹	X	X	X	X	X	X	X
PK blood sample ¹²		X				X	
PK urine sample ¹³		X				X	
Body surface area ¹⁴		X					
CPX-POM infusions ¹⁵		X	X	X	X	X	
TURBT ¹⁶						X	

Abbreviations: AE = adverse event; ALT = alanine aminotransferase; aPTT = activated partial thromboplastin time; AST = aspartate aminotransferase; BSA = body surface area; BUN = blood urea nitrogen; CPX-G = ciclopirox glucuronide; CPX-POM = ciclopirox phosphoryloxymethyl ester; CT = computed tomography; D = day; ECG = electrocardiogram; ECOG = Eastern Cooperative Oncology Group; EDTA = ethylenediamine tetraacetic acid; eGFR = estimated glomerular filtration rate; ELISA = enzyme linked immunosorbent assay; ET = early termination; GGT = gamma glutamyl transferase; IV = intravenous; LC-MS/MS = liquid chromatography-tandem mass spectrometry; MUGA = multi-gated acquisition; PD = pharmacodynamic; PK = pharmacokinetic; PT = prothrombin time; QTc = corrected QT interval; RBC = red blood cell; RC = radical cystectomy; SAE = serious adverse event; TURBT = transurethral resection of a bladder tumor; V = visit; WBC = white blood cell.

1. Safety follow-up assessments will be performed within 30 days (± 3 days) after the last dose of CPX-POM. Or, in the event that a patient discontinues from the study prematurely, the site will make every effort to perform the assessments listed for this study visit.
2. Pregnancy tests will be required only for women of childbearing potential at Screening and before dosing on Day 1. Urine or serum pregnancy tests are acceptable.

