3. Pre-treatment bladder tumor tissue sample will be obtained during in-office cystoscopy by cold cup biopsy within 4 weeks of TURBT. Post-treatment bladder tissue sample will be obtained at surgical resection (TURBT) on Day 5.
4. Hematology will include measurement of hemoglobin, hematocrit, platelets, RBC, reticulocytes, and WBC with differential.
5. Clinical chemistry will include measurement of potassium, sodium, chloride, glucose, BUN, creatinine, creatinine clearance, ALT, AST, GGT, alkaline phosphatase; indirect bilirubin, direct bilirubin, total bilirubin, total protein, albumin, calcium, bicarbonate, magnesium, phosphate, lipase, and amylase.
6. Urinalysis will include color, turbidity, pH, specific gravity, glucose, ketones, nitrites, bilirubin, urobilirubin, protein, RBCs, WBCs, epithelial cells, casts, crystals, and bacteria, and eGFR at Screening only.
7. A full physical examination will be conducted at Screening and at Visit 7/Follow-up. At each other study visit, patients will be assessed for continued dosing and any possible physical symptoms/toxicities and a physical examination may be performed, if indicated. Body weight should be measured at each study visit. Height should be measured at Screening.
8. Vital signs will be measured before any blood draws scheduled for the same time point. Vital signs will include blood pressure, respiratory rate, pulse, oxygen saturation, and temperature.
9. At Screening, 12-lead ECGs will be performed in triplicate, with each measurement separated by 2 minutes. The average of the 3 screening ECGs will be used to calculate QTc interval to determine study eligibility. Thereafter, single 12-lead ECGs will be performed for all patients prior to drug administration on Days 1 and 5 and at the Final Study visit.
10. All AEs and SAEs will be collected from the signing of the informed consent form through the time of TURBT. Starting at TURBT, only AEs related to CPX-POM treatment should be recorded; AEs related to the TURBT will not need to be recorded.
11. All concomitant medications will be recorded from the time of Screening up to the time of TURBT. Starting at TURBT, only medications associated with an AE related to CPX-POM treatment need to be recorded; routine medications and medications associated with the TURBT procedure do not need to be recorded.

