CPX-POM was well tolerated up to the MTD of 900 mg/m². At the MTD, all of the related adverse events (AEs) were Grade 1 in severity. Nausea and vomiting were the most frequently reported treatment-emergent adverse events (TEAEs), reported by 6 and 8 patients, respectively, and were more common in the higher dose cohorts. The primary dose limiting toxicity was central nervous system (CNS)-related side effects, in particular a drug-related serious adverse event (SAE) of Grade 3 confusion in the 1200 mg/m² cohort, which was considered a dose limiting toxicity, and 4 AEs of Grade 1 confusion in the 600 and 900 mg/m² cohorts (i.e., 2 reports in each cohort). In the Nervous System system organ class (SOC), amnesia, dizziness, headache, and somnolence were also reported by 2 patients each. One patient in the 30 mg/m² dose cohort died during the study as a result of an SAE of pneumonia, which started on Study Day 28 and was considered not related to CPX-POM treatment.

During the Study CPX-POM-001 Dose Escalation Cohorts, CPX-POM injections were completed over a 10-minute period. During the present study, injections will be completed over a 20-minute period. Slowing the speed of CPX-POM injection may reduce the frequency and severity of CNS-related side effects such as confusion and infusion-related reactions.

There was no evidence of corrected QT interval (QTc) prolongation or other ECG abnormalities in any patient receiving CPX-POM doses up to 1200 mg/m².

CPX-POM was rapidly and completely metabolized to CPX. Plasma CPX-POM concentrations were observed in patients, however, concentrations declined rapidly, falling below the lower limits of the assay within 2 hours. CPX-POM was not detected in urine. Analysis of PK data showed that systemic exposure to CPX increased proportionately with increasing dose. The apparent elimination half-life of CPX typically ranged from 2 to 6 hours across the dose range studied. There was relatively low overall variability (<30%) in systemic clearance among individual patients. There was no indication of accumulation over the 5 days of CPX-POM dosing (mean area under the concentration-time curve at steady state (AUC_{ss})/initial area under the concentration-time curve (AUC_i) = 1.03). At the MTD, approximately 8.5% of the CPX-POM dose was excreted as CPX. The mean urine concentrations of CPX over 24 hours were >200 µM at the MTD.

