2.2. Background on Bladder Cancer and Rationale for the Study

The purpose of this study is to characterize the safety and mechanisms of action of CPX-POM in patients with newly diagnosed or recurrent, untreated or intravesical treatment completed >6 months before the current diagnosis, resectable bladder tumors.

Bladder cancer is the sixth most common solid tumor in the United States with an estimated 80,479 new cases and 17,670 deaths in 2019 ([American Cancer Society, 2019](#)). In 2016, there were an estimated 699,450 people living with this disease in the United States ([Siegel et al, 2019](#)). The disease has a high risk of recurrence as well as progression, thus requiring

life-long surveillance, making bladder cancer one of the most expensive cancers to treat on a per-patient-lifetime-basis (Botteman et al, 2003; Yeung et al, 2014). While the overall 5-year survival rate for bladder cancer is 77%, in those with advanced disease, this rate can be as low as 4% (NCI SEER Cancer Stat Facts, 2019).

Bladder cancer is defined as two diseases, each with different treatment approaches as well as outcomes. Seventy percent or more of newly diagnosed patients have non-muscle invasive bladder cancer (NMIBC) which is generally considered less life-threatening than muscle invasive bladder cancer (MIBC) (Heneý, 1992). However, in spite of endoscopic resection followed by intravesical immunotherapy (Bacillus Calmette-Guérin [BCG]) or chemotherapy (e.g., mitomycin C, gemcitabine), 60 to 70% of those with NMIBC will recur and 20 to 30% will progress to MIBC (Aldoursari and Kassouf, 2010), where the gold standard treatment is radical cystectomy (RC) coupled with cisplatin-based chemotherapy in either neoadjuvant or adjuvant settings (Milan-Rodriguez et al, 2000). It is estimated, however, that as many as 40 to 50% of MIBC patients are ineligible for cisplatin chemotherapy due to impaired renal function (Dash et al, 2006). Patients with impaired performance status (Eastern Cooperative Oncology Group [ECOG] >1), heart failure (New York Heart Association [NYHA] class \geq III), grade \geq 2 hearing loss, and/or grade \geq 2 neuropathy are also ineligible for cisplatin-based chemotherapy. Given the poor complete response rate associated with neoadjuvant carboplatin and gemcitabine (Peyton et al, 2018), cisplatin-ineligible MIBC patients go straight to RC or enroll in clinical trials.

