6.2. Prior and Concomitant Medications

Medications taken within 30 days before baseline (Study Visit 2) must be recorded as prior medications.

Prohibited concomitant medications include any anti-cancer agents, steroids, any iron replacement therapy, warfarin, or any drug known to have significant nephrotoxicity. A minimum of 10 days between termination of the prohibited concomitant medications or a duration of five elimination half-lives will be required prior to administration of IV CPX-POM to eligible patients. Concomitant radiation therapy is also prohibited.

Note that anti-emetics such as ondansetron or granisetron are allowed if used with caution and attention to the approved labelling.

All concomitant medications will be recorded from the time of Screening up to the time of TURBT. Routine medications associated with the cystectomy procedure do not need to be recorded. Starting at the time of TURBT, only medications associated with an AE related to CPX-POM treatment need to be recorded.

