### 7.2 Protocol Deviations

Major protocol deviations that could potentially affect the efficacy or safety conclusions of the study will be identified prior to database lock.

Major protocol deviations will be summarized by deviation category and listed.

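### Anticancer therapy begun between TURBT and the Day 35 visit need not enter the study database, so the Day 35 laboratory, vital-sign and ECG summaries are not assured of identifying values taken after it (minor)

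*Protocol*

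**What the plan says.** **Recording rule.** All concomitant medications are recorded from Screening to TURBT. After that, Table 1 footnote 11 says: "Starting at TURBT, only medications associated with an AE related to CPX-POM treatment need to be recorded". It adds that "routine medications and medications associated with the TURBT procedure do not need to be recorded". Protocol 6.2 agrees: "Starting at the time of TURBT, only medications associated with an AE related to CPX-POM treatment need to be recorded". Neither text treats anticancer therapy separately, and no form for subsequent therapy is described.

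**Prohibition.** Protocol 6.2 also states: "Prohibited concomitant medications include any anti-cancer agents". It sets a washout before CPX-POM but does not say when the prohibition ends.

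**Disease background.** Protocol 2.2 describes care for non-muscle-invasive disease as "endoscopic resection followed by intravesical immunotherapy" or chemotherapy, without giving an interval.

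**Day 35.** Table 1 footnote 1 says: "Safety follow-up assessments will be performed within 30 days", with a window of 3 days either way, counted from the last dose. Haematology, chemistry, urinalysis, vital signs and ECG are all scheduled at that visit.

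**Analysis.** SAP 9.5, 9.6 and 9.8 give descriptive statistics and changes from baseline at every post-baseline time point, and 9.8 adds an ECG shift table to follow-up. SAP 7.4 lists prior and concomitant medications. It defines concomitant as started on or after, or ongoing at, the start of treatment, with no cut-off at TURBT. SAP 7.2 covers deviations: "Major protocol deviations that could potentially affect the efficacy or safety conclusions of the study will be identified prior to database lock".

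**The concern.** The primary objective is safety and dose tolerance, and Day 35 is the only scheduled visit after the day of surgery. It supplies the only ECG after the fifth dose (the Day 5 ECG is taken before dosing) and the only urinalysis after Day 3.

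If a patient has begun another anticancer drug by then, that drug is the more recent exposure. A change in, say, a blood count or creatinine could come from it. TURBT also affects Day 35 values, but it happens to every patient at a known time. A new therapy may be started in some patients and not others, on dates the database need not hold.

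The SAP 7.4 definition adds a risk of misreading. Because it has no cut-off at TURBT, its listing would look complete through Day 35, although the collection rule does not feed it after Day 5.

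**Working it through.** The plan gives no figure to reproduce: SAP 4 states that there was no formal sample size calculation. The check is mainly a comparison of texts, with some arithmetic for scale.

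**1. Would another route capture the therapy with a date?**

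| Route | What it provides | Dated drug record required in the database? |
|---|---|---|
| Footnote 11 and 6.2 | Drugs associated with a CPX-POM-related AE | Only for those drugs |
| 6.2 prohibition, if it runs to Day 35 | Use is a deviation; listed under SAP 7.2 if judged major | No |
| 6.2 prohibition, if it ends earlier | Use is permitted | No |
| SAP 9.10 TURBT listing | Might hold an instillation given at surgery | Not for therapy begun later |
| Protocol 10.2.5 source data | Concomitant medication with start and end dates, at the site | No |

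The AE route is weakest where it is most needed. If the investigator attributes a Day 35 abnormality to the new therapy, the event is not CPX-POM-related, and footnote 11 then asks for no record of the drug.

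**2. Is the exposure limited to topical treatment?** Protocol 2.2 describes systemic cisplatin-based chemotherapy, before or after cystectomy, for muscle-invasive disease. The criteria in 5.1 and 5.2 require a cystoscopically confirmed tumour scheduled for TURBT and do not exclude muscle-invasive tumours. Systemic therapy therefore cannot be ruled out from the documents, though they give no timing for it.

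**3. Share of the observation period under the restricted rule.** With f the days from TURBT to follow-up and 4 days from first dose (Day 1) to TURBT (Day 5), share = f / (f + 4).

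- Nominal Day 35: f = 35 − 5 = 30, so 30/34 = 88.2%.
- Footnote 1 window (30 ± 3 days): 27/31 = 87.1% to 33/37 = 89.2%.
- Protocol 8.1.1.2 window (28 ± 5 days): 23/27 = 85.2% to 33/37 = 89.2%.

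This is time under restricted recording, not time on another therapy.

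**4. Is CPX still present at Day 35?** Protocol 2.1 reports: "The apparent elimination half-life of CPX typically ranged from 2 to 6 hours across the dose range studied". Thirty days is 30 × 24 = 720 hours, so 720/6 = 120 to 720/2 = 360 half-lives. Exposure ended long before the visit.

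**5. Leverage in 12 patients.** Assumption for illustration: k of 12 patients start a therapy, and it shifts their Day 35 value by d on average. The mean change then moves by k × d / 12.

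| k | Shift in mean change |
|---|---|
| 0 | 0 |
| 1 | 0.083d |
| 3 | 0.25d |
| 6 | 0.50d |
| 12 | d |

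One patient changing category moves a 12-patient ECG shift table by 1/12 = 8.3 percentage points. Neither k nor d can be obtained from the documents.

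**6. Outputs not affected.** The graded laboratory table in SAP 9.5 stops at the last dose. On-treatment data before TURBT are under full recording.

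**The case against.** The strongest reply is that nothing shows the event would happen. Protocol 2.2 gives general background with no interval, so the step from therapy after resection to therapy before Day 35 is not in the documents. Protocol 2.2 also describes currently available agents as intravesical, and topical treatment gives little reason to expect a change in chemistry, vital signs or ECG. Surgery precedes every Day 35 value, the study has one arm and no hypothesis tests, and the Day 35 mean change could not be attributed to CPX-POM even with perfect recording. With one planned centre and about 12 patients, an odd value can be queried.

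Most of this stands, and it limits the point to a minor one. The topical argument does not dispose of it, because muscle-invasive tumours are not excluded and systemic therapy is described for them. The query route depends on someone noticing the value and going back to source.

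A reader might infer that the Day 35 summaries cannot identify these patients at all. The documents do not support that. Footnote 11 sets a minimum, Table 1 still schedules concomitant medications at Day 35, and SAP 7.4 lists whatever is entered. Source records should hold the dates, and a deviation listing may show the use. The accurate statement is that identification is not required, and so not assured.

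**Conclusion.** The point holds as a gap in required data capture. The recording rule is explicit, appears twice and has no exception for anticancer therapy. The partial backups do not guarantee a dated drug record in the study database. The outputs concerned are the Day 35 descriptive and change-from-baseline summaries in SAP 9.5, 9.6 and 9.8, including the ECG shift table.

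The size cannot be estimated. The number of patients affected could be anything from 0 to 12, the shift per patient is unknown, and the effect may be zero. The 88% and 8.3-point figures show opportunity and leverage. A reader might take them as evidence of bias, but the documents give no frequency, timing or effect size to support that.

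The point does not extend usefully to the AE tables: drugs associated with a recorded CPX-POM-related AE are already captured. Whether unrelated AEs after TURBT are collected, on which footnote 10 conflicts with Protocol 8.1.1.1 and 8.1.1.2, is a separate question that this change does not settle.

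Severity: minor, a cheap improvement.

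**What to change.** - **Table 1 footnote 11 and Protocol 6.2:** require agent, route and start date for any anticancer therapy, intravesical or systemic, begun from TURBT through the Follow-up visit, whether or not an AE occurs. Keep other routine and TURBT-related medications exempt.
- **Protocol 6.2:** state when the prohibition on anti-cancer agents ends, so that it is clear whether such use is a deviation.
- **SAP 7.4:** list these therapies.
- **SAP 9.5, 9.6 and 9.8:** flag Day 35 laboratory, vital-sign and ECG values taken on or after the start of such a therapy. No AE flag in SAP 9.4 is needed.

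The cost is a short protocol amendment with the usual IRB notification, one CRF line, edits to four SAP sections and slightly more data entry. If patients have already passed Day 35, the dates should be retrievable from site source records.

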2. INTRODUCTION

2.1. Background on CPX-POM

Fosciclopirox (CPX-POM) is a prodrug of ciclopirox (CPX). CPX is a synthetic antifungal agent approved for topical dermatologic use in the treatment of a broad spectrum of fungal organisms (Gupta, 2001). CPX and ciclopirox olamine (CPX-O) are contained in a number of marketed topical drug products. CPX also exerts antibacterial activity against many Gram-positive and Gram-negative bacteria (Abrams et al, 1991). CPX is a hydroxypyridone that is structurally unrelated to other antifungal agents and has a unique and complex mode of action. CPX is thought to act through the chelation of polyvalent metal cations, such as iron and aluminum, resulting in the inhibition of the metal-dependent enzyme systems (e.g., cytochromes, catalase, peroxidase), thus disrupting cellular activities, such as inhibiting degradation of peroxides within the fungal cells (Gupta and Plott, 2004) and mitochondrial electron transport processes and energy production (Sakurai et al, 1978; Gupta et al, 1994). It is also thought that CPX affects the cytoplasmic membranes, inhibiting transport of essential elements in the fungal cell, disrupting the synthesis of DNA, ribonucleic acid (RNA), and protein (Gupta and Plott, 2004). In addition, CPX may have anti-inflammatory activity as demonstrated by its ability to inhibit the synthesis of prostaglandins and leukotrienes in human polymorphonuclear cells (Abrams et al, 1991) and to inhibit the formation of 5-lipoxygenase and ciclo-oxygenase (Bohn and Kraemer, 2000; Hanel et al, 1991).

CPX has demonstrated in vivo and/or in vitro anticancer activity in at least 17 types of solid tumor and hematologic cancers (CPX-POM Investigators Brochure, 2017). CPX modulates iron-dependent enzymes and signaling pathways resulting in inhibition of cell growth, proliferation, and survival. CPX has been demonstrated to chelate intracellular iron in human cancer cells (Kwong et al, 2015; Eberhard et al, 2009; Sidarovich et al, 2015), which plays an important role in cancer cell death resulting from exposure to CPX (Clement et al, 2002; Szüts and Krude, 2004; Eberhard et al, 2009; Sidarovich et al, 2015). CPX exposure altered expression of 54 proteins in stem cells, including those associated with nucleotide binding, biosynthetic processes, gene expression, regulation of transcription, cell cycle processes, RNA and messenger RNA (mRNA) processing, and embryonic development (Dihazi et al, 2011).

CicloMed is aware of 2 published reports of CPX-O administered orally to humans (Minden et al, 2014; Kellner et al, 1981). Following oral administration of CPX-O to patients with refractory hematologic malignancies, evidence of pharmacodynamic (PD) activity was observed (Minden et al, 2014; Song et al, 2011). Administration by the oral route of administration, however, is not feasible because of dose-limiting gastrointestinal toxicity and poor oral bioavailability due to high first pass effect (Minden et al, 2014).

Scientists at the University of Kansas synthesized the phosphoryloxymethyl ester of CPX, CPX-POM to enable parenteral administration of CPX. In contrast to CPX and CPX-O, CPX-POM has high water solubility and is readily formulated for parenteral administration.

Pharmacokinetic (PK) studies in laboratory animals showed that CPX-POM is rapidly and completely metabolized to its active metabolite, CPX, which then disappears from plasma following systemic administration of CPX-POM. Following systemic administration of CPX-POM, the dose is eliminated from the body via renal clearance of CPX and the inactive glucuronide metabolite of CPX (CPX-G).

In rats, intravenous (IV) CPX-POM administered for 28 consecutive days did not cause mortality or changes in body weight, food consumption, ophthalmology, hematology, coagulation, clinical chemistry, urinalysis, or organ weights. There were no test item-related findings grossly or microscopically at the highest dose level tested (50 mg/kg/day). Test item-related transient clinical signs, including slight to moderate decreased activity, increased respiration, eating-like behavior, and slight to moderate incoordination were noted immediately after dosing at 50 mg/kg/day. The no observed adverse effect level (NOAEL) in rats was 25 mg/kg/day in males and 50 mg/kg/day in females.

In dogs, CPX-POM administered for 28 consecutive days did not cause mortality or changes in body weight, food consumption, electrocardiogram (ECG) parameters, hematology, coagulation, clinical chemistry, urinalysis, or organ weights. There were no test item-related findings grossly or microscopically at dose levels up to 30 mg/kg/day. Test item-related transient clinical signs such as salivation, fecal changes, aggression, shaking, and tremors were noted after dosing at the highest dose level tested on the study (30 mg/kg/day). Convulsion was apparent in one dog on a single occasion. Test-item related ophthalmic changes were noted in 3/10 dogs treated with 30 mg/kg/day. Thus, the NOAEL in dogs was determined to be 10 mg/kg/day and the highest non-serious toxic dose (HNSTD) in the dog was determined to be 30 mg/kg.

The first study of CPX-POM in patients (Study CPX-POM-001) has been initiated. A total of 19 patients with a histologically- or cytologically-confirmed solid tumor refractory to standard therapy were enrolled in the Dose Escalation cohorts, 6 males and 13 females ranging in age from 20 to 86 years. The starting dose of CPX-POM was 30 mg/m² administered once per day on Days 1 to 5 of each 21-day cycle. Doses were escalated per protocol up to 1200 mg/m². The number of cycles of CPX-POM administered ranged from 1 to 6 per patient (mean = 2.5 cycles). The maximum tolerated dose (MTD) was determined to be 900 mg/m², which was administered to a total of 6 patients. The safety, dose tolerance, PK, and PD of IV CPX-POM, administered at the MTD over 20 minutes are currently being characterized in an expansion cohort of 12 patients with muscle invasive bladder cancer scheduled for cystectomy.

CPX-POM was well tolerated up to the MTD of 900 mg/m². At the MTD, all of the related adverse events (AEs) were Grade 1 in severity. Nausea and vomiting were the most frequently reported treatment-emergent adverse events (TEAEs), reported by 6 and 8 patients, respectively, and were more common in the higher dose cohorts. The primary dose limiting toxicity was central nervous system (CNS)-related side effects, in particular a drug-related serious adverse event (SAE) of Grade 3 confusion in the 1200 mg/m² cohort, which was considered a dose limiting toxicity, and 4 AEs of Grade 1 confusion in the 600 and 900 mg/m² cohorts (i.e., 2 reports in each cohort). In the Nervous System system organ class (SOC), amnesia, dizziness, headache, and somnolence were also reported by 2 patients each. One patient in the 30 mg/m² dose cohort died during the study as a result of an SAE of pneumonia, which started on Study Day 28 and was considered not related to CPX-POM treatment.

During the Study CPX-POM-001 Dose Escalation Cohorts, CPX-POM injections were completed over a 10-minute period. During the present study, injections will be completed over a 20-minute period. Slowing the speed of CPX-POM injection may reduce the frequency and severity of CNS-related side effects such as confusion and infusion-related reactions.

There was no evidence of corrected QT interval (QTc) prolongation or other ECG abnormalities in any patient receiving CPX-POM doses up to 1200 mg/m².

CPX-POM was rapidly and completely metabolized to CPX. Plasma CPX-POM concentrations were observed in patients, however, concentrations declined rapidly, falling below the lower limits of the assay within 2 hours. CPX-POM was not detected in urine. Analysis of PK data showed that systemic exposure to CPX increased proportionately with increasing dose. The apparent elimination half-life of CPX typically ranged from 2 to 6 hours across the dose range studied. There was relatively low overall variability (<30%) in systemic clearance among individual patients. There was no indication of accumulation over the 5 days of CPX-POM dosing (mean area under the concentration-time curve at steady state (AUC_{ss})/initial area under the concentration-time curve (AUC_i) = 1.03). At the MTD, approximately 8.5% of the CPX-POM dose was excreted as CPX. The mean urine concentrations of CPX over 24 hours were >200 µM at the MTD.

